11.4. Statistical Analyses

For each of the primary and secondary efficacy and safety endpoints, appropriate summary statistics (e.g., event rate) including 95% confidence interval (CI) will be provided.

For each of the endpoints, the time from reference date to the first occurrence of an event (based on CEC adjudication), is analyzed using a Cox proportional hazard model with treatment regimen as a factor and all the stratification factors from the randomization (IXRS) as covariates, dose adjustment [yes, no], to provide point estimates and 95% CI for the hazard ratio (HR). Depending on the analysis period used in the statistical analysis, subjects without an occurrence of an event will be censored at the last date of the analysis period or at the last date of known outcomes status. The latter is determined on an individual basis for subjects with incomplete follow-up.

The parameter estimate β ($= \ln(\text{Hazard ratio})$), its standard error, p-value, and 95% confidence limits are calculated according to the maximum partial likelihood method, with Breslow's approximation for ties (SAS PHREG procedure).

For time to first event analyses, cumulative event rates over time are summarized using the Kaplan-Meier method as appropriate.

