5.1.2. Method of Treatment Allocation

Prior to randomization of a subject, all eligibility criteria must be met and a signed informed consent obtained.

Enrollment and randomization must occur between the evening of the day of TAVI and 5* days, i.e., until 23:59 of the 5th* day provided that the TAVI procedure has been judged as successful (See inclusion criteria #1 for definition of successful TAVI) and the subject is qualified based on all the protocol defined inclusion/exclusion criteria. All sites will be required to maintain a record of all subjects screened for the trial. The reason for screen failure must be documented in the subject's records. Subjects must be randomized without delay and administered their first dose of study medication within 24 hours post randomization; however, NO EARLIER than the morning after successful TAVI. Randomization will be performed using the IXRS system for subjects meeting all eligibility criteria. The directions on how to use the system will be provided in the IXRS Quick Reference Manual. The randomization scheme will be securely stored at the statistical department of the database management center.

*If subject is waiting on a decision on pacemaker surgery, then can extend to 7 (7th) days

Based on this information, the system will assign a unique subject identification number and treatment for that subject. Trial randomization will not be blinded and once subject is assigned to a treatment arm, no treatment cross-over is permitted. Subjects will be randomly assigned in a 1:1 ratio to receive Edoxaban or VKA. The Investigator will pre-declare the type (if any) P2Y₁₂ antagonist or ASA treatment and its projected last dose prior to the randomization (pre-declaration, via the IXRS).

The Investigator's knowledge of the treatment must not influence the decision to enroll a particular subject or affect the order in which subjects are enrolled.

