6.2. Randomization Visit (Day 1)

Randomization must take place within the evening of the day of TAVI and 5* days, i.e., until 23:59 of the 5th* day provided that the TAVI procedure has been judged as successful (See inclusion criteria #1 for definition of successful TAVI), and the subject is qualified based on all the protocol defined inclusion/exclusion criteria. Randomization should occur as soon as possible after signing the informed consent, given eligibility is confirmed.

*If subject is waiting on a decision on pacemaker surgery, then can extend to 7 (7th) days

- Check subject against inclusion/exclusion criteria including the most recent lab results.
- Record type of TAVI device inserted into subject in the eCRF

- Enter elements for EuroSCORE 1, EuroSCORE 2, Society of Thoracic Surgeons (STS), CHAD, and HAS-Bleed scores into the eCRF
- Contact IXRS for randomization and pre-declaration of OAP.
- Prior to any study drug administration or other tests, the subject must complete the PACT-Q1 and EuroQoL (EQ-5D-5L) questionnaires. These will be collected and uploaded into the data base by the CRO via the eCRF.
- If ECG was performed as part of routine medical practice, record the results. If not obtained as part of routine medical practice, collect a pre-dose ECG for baseline measurement and record results.
- Update medical / surgical history (including bleeding history) since screening
- Physical Examination including
 - Record vital signs (blood pressure and heart rate after the subject has been resting at least 5 minutes in a sitting position; body temperature, and weight)
 - Record height
- Record prior (since screening) medications and review as per exclusion criteria.
- If echocardiogram (transthoracic echo [TTE] or transesophageal echo [TEE]) was performed pre-TAVI per local standard of care, the information will be recorded as specified in the eCRF.

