11.4.1. Analysis of the primary endpoint(s)

The primary efficacy endpoint is *NACE*, i.e., the composite of all-cause death, MI, ischemic stroke, SEE, valve thrombosis, and major bleeding (ISTH definition).

The primary safety endpoint is *major bleeding (ISTH definition)*.

There are 4 primary hypotheses that will be tested in hierarchical order:

- Hypothesis (1):
 - The Edoxaban-based regimen is noninferior to the VKA-based regimen with regards to NACE.
- Hypothesis (2):
 - The Edoxaban-based regimen is noninferior to the VKA-based regimen with regards to major bleeding (ISTH definition).
- Hypothesis (3):
 - The Edoxaban-based regimen is superior to the VKA-based regimen with regards to major bleeding (ISTH definition).
- Hypothesis (4):
 - The Edoxaban-based regimen is superior to the VKA-based regimen with regards to NACE.

The analysis set and analysis periods to be used for the main analysis related to these four hypotheses are presented below:

Table 11.1: Statistical Analysis Hierarchy for Primary Parameters

Hypothesis	Endpoint	Primary Analysis Set	Primary Analysis Period
(1)	NACE	ITT	Overall study period
(2)	Major bleeding (ISTH def)	ITT	Overall study period
(3)	Major bleeding (ISTH def)	ITT	Overall study period
(4)	NACE	ITT	Overall study period

To control the type-I error rate, these four hypotheses will be tested in a hierarchical manner:

- Step (1): The Edoxaban-based regimen will be considered noninferior to the VKA-based regimen with regards to NACE, if the upper boundary of the two-sided 95% CI for hazard ratio (HR) falls below 1.38. If it is significant, then go to Step (2), otherwise stop here.
- Step (2): The Edoxaban-based regimen will be considered noninferior to the VKA-based regimen with regards to major bleeding (ISTH def.), if the upper boundary of the two-sided 95% CI for HR falls below 1.38. If it is significant, then go to Step (3), otherwise stop here.
- Step (3): The Edoxaban-based regimen will be considered superior to the VKA-based regimen with regards to major bleeding (ISTH def.), if the upper boundary of the two-sided 95% CI for HR falls below 1.00. If it is significant, then go to Step (4), otherwise stop here.
- Step (4): The Edoxaban-based regimen will be considered superior to the VKA-based regimen with regards to NACE, if the upper boundary of the two-sided 95% CI for HR falls below 1.00.

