For each of the primary and secondary adjudicated endpoints, appropriate summary statistics (e.g., event rate) including 95% CI will be provided.

For each of the adjudicated endpoints, the time from reference date to the first occurrence of an event (based on CEC adjudication), is analyzed using a Cox proportional hazard model with treatment regimen as a factor and all the stratification factors from the randomization (IXRS) [dose adjustment [yes, no]] as covariates, to provide point estimates and 95% Confidence Interval (CI) for the hazard ratio (HR). Depending on the analysis period used in the statistical analysis, subjects without an occurrence of an event

will be censored at the last date of the analysis period or at the last date of known outcomes status. The latter is determined an individual basis for subjects with incomplete follow-up.

To evaluate the robustness of the primary analyses, the analyses will be repeated using the mITT and PP analysis set. In addition, the statistical results based on the following analysis periods: 'initial dose to final dose + 30 days' and 'overall study period + 30 days' will be presented and will be interpreted in a more descriptive way. Results for other combinations of analysis sets and analysis periods may be presented if considered necessary.

For time to first event analyses based, cumulative event rates over time are summarized using the Kaplan-Meier method as appropriate.

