11.9. Sample Size Determination

In order to determine the sample size, the following assumptions were made:

- *Event rate*: Based on published literature and results from the ENGAGE AF-TIMI 48 study, it is assumed that the event rate of the primary efficacy endpoint of NACE in AF-subjects with TAVI treated with VKA would be 14%/year.
- *Noninferiority margin*: No data were available for placebo-controlled studies in this subject population. The Executive Committee reviewed all available data including practice changes observed in other areas of cardiology on the basis of clinical trials and the level of statistical certainty they had achieved. Then it made the judgment that a noninferiority margin for hazard ratio 1.38 would be accepted by the medical community for a practice change given the fact that other trials have already supported the use of Edoxaban in subjects warranting anticoagulation and its related regulatory approval for human use in the participating countries.
- *Significance level for statistical testing*: 0.05.
- *Observed hazard ratio*: 0.95.

With the above assumptions, to demonstrate noninferiority with 80% of power, the study needs to collect at least 320 NACE across the combined study arms. With an anticipated median follow-up time of two years and an annual event rate of 14%, a total of approximately 1400 subjects need to be randomized.

The sample size is event driven. The sample size or the duration of follow-up may require adjustment based on the actual versus anticipated primary endpoint event and drop-out rates.

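### The primary Cox model leaves out baseline predictors the trial already records, which costs a little power and leaves unclear which hazard ratio the 1.38 margin refers to

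*Combined protocol and SAP*

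**What the plan says.** Section 11.4 analyses each endpoint with a Cox model "with treatment regimen as a factor and all the stratification factors from the randomization (IXRS) as covariates, dose adjustment [yes, no"]. Section 11.4.1 repeats this model for the primary endpoints, with "all the stratification factors from the randomization (IXRS) [dose adjustment [yes, no]] as covariates". Dose adjustment is the only factor named. The noninferiority decision for NACE is taken on this hazard ratio, "if the upper boundary of the two-sided 95% CI for hazard ratio (HR) falls below 1.38", and the same limit is used for major bleeding.

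Two other sets of baseline information are collected. Under section 5.1.2 the investigator declares any P2Y12 "antagonist or ASA treatment and its projected last dose prior to the randomization (pre-declaration, via the IXRS"). Section 6.2 instructs sites at the randomization visit: "Enter elements for EuroSCORE 1, EuroSCORE 2, Society of Thoracic Surgeons (STS), CHAD, and HAS-Bleed scores into the eCRF". Neither appears in the model. The robustness analyses named in section 11.4.1 change the analysis set and the analysis period, not the covariates.

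Section 11.9 presents the margin as a judgment of the Executive Committee, that a "noninferiority margin for hazard ratio 1.38 would be accepted by the medical community". It does not say whether the ratio is conditional on any baseline risk.

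**The concern.** The protocol itself treats antiplatelet therapy as a bleeding risk. Section 1.3 says that adding antiplatelet agents to oral anticoagulation raises bleeding. Section 1.1 reports more major and life-threatening bleeding with dual than with single antiplatelet therapy. Section 3.2 puts the stenting scenario at 25-34% of TAVI patients or more, so declared therapy should vary. Major bleeding is the endpoint of H2 and H3 and a component of NACE.

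A Cox model that omits a strong predictor estimates a hazard ratio closer to 1 than the ratio conditional on that predictor. For superiority, this lowers power; H4 can be tested only if H3 succeeds, so a loss at H3 carries forward. For noninferiority, it matters which of the two ratios is held against 1.38, and the plan does not say.

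**Working it through.** **Inputs from the documents.** 1:1 allocation (5.1.2); margin 1.38, planning hazard ratio 0.95, 14% per year on VKA, about 1400 subjects, 320 NACE, 80% power (11.9); upper limit of the two-sided 95% CI as the criterion (11.4.1).

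**Assumptions, not in the documents.** Baseline risk is a normal score on the log-hazard scale with SD 0.5, 0.75 or 1.0 (c-statistic about 0.63, 0.69, 0.74). For H3, the hazard ratio is 0.65 and the number of bleeds is assumed. The simulated adjustment uses the whole score, and the dose-adjustment covariate is not simulated. Both choices overstate what the real covariates would gain.

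**1. The plan's own figure.** Events = 4(1.960 + 0.842)² / [ln(1.38/0.95)]² = 31.40 / 0.1394 = 225.2, so 226, not 320. At 320 events the power is 91.6%. This mismatch is a separate matter and does not affect what follows.

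**2. NACE noninferiority.** 3000 simulated trials per row; control 2-year risk 1 − exp(−0.28); follow-up uniform from 0.5 to 3 years; about 290 to 345 events.

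| True HR given the score | Score SD | Mean HR, score omitted | Mean HR, score adjusted | Noninferior, omitted | Noninferior, adjusted |
|---|---|---|---|---|---|
| 0.95 | 0.5 | 0.955 | 0.953 | 88.6% | 89.0% |
| 0.95 | 0.75 | 0.956 | 0.952 | 88.0% | 88.4% |
| 0.95 | 1.0 | 0.958 | 0.951 | 87.6% | 88.9% |
| 1.00 | 0.5 | 1.001 | 1.001 | 78.4% | 78.5% |
| 1.00 | 0.75 | 1.002 | 1.002 | 79.0% | 78.2% |
| 1.00 | 1.0 | 1.001 | 1.001 | 78.1% | 79.0% |
| 1.38 | 0.5 | 1.363 | 1.382 | 3.1% | 2.3% |
| 1.38 | 0.75 | 1.342 | 1.382 | 4.6% | 2.4% |
| 1.38 | 1.0 | 1.315 | 1.381 | 6.9% | 2.6% |

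The standard error hardly changes with adjustment (0.1173 against 0.1174 at HR 0.95, SD 0.5). Adjustment works by moving the estimate away from 1, not by narrowing the interval.

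**3. Hand check of the last three rows.** False noninferiority ≈ Φ(−1.960 + [ln 1.38 − ln HR(omitted)] / SE).
- SD 0.5: (0.3221 − 0.3097)/0.1091 = 0.114; Φ(−1.846) = 3.2%.
- SD 0.75: (0.3221 − 0.2942)/0.1093 = 0.255; Φ(−1.705) = 4.4%.
- SD 1.0: (0.3221 − 0.2738)/0.1095 = 0.441; Φ(−1.519) = 6.4%.

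These agree with the simulation. With SD 0.5 and 0.7 under 3-year accrual and 5% yearly loss, the rates were 3.2% and 3.6% with the score omitted, against 2.4% and 2.2% adjusted.

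**4. The same test judged against its own hazard ratio.** The true conditional ratio was raised until the model without the score estimates 1.38, which needs about 1.40, 1.42 and 1.46. False noninferiority was then 2.8%, 2.7% and 2.9% (6000 trials each), close to the nominal 2.5%.

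**5. H3 power at hazard ratio 0.65.** As a benchmark with 136 bleeds: z = 0.4308 × √136 / 2 = 2.512, and Φ(2.512 − 1.960) = 71%. Simulated power, score omitted and then adjusted:
- about 136 bleeds: 67.8% to 69.2% (SD 0.5) and 66.4% to 69.6% (SD 0.7), gains of 1.4 and 3.2 points;
- about 123 bleeds: 66.3% to 67.4% and 61.6% to 64.4%, gains of 1.1 and 2.8 points.

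Over runs with about 130 to 143 bleeds the gain was 0.4 to 3.6 points. The smallest gains are within simulation error.

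**The case against.** The strongest reply is that nothing is broken. Allocation is randomized, so omitting baseline covariates causes no confounding. A pre-specified Cox model with the stratification factor is a sound primary analysis. The shift toward 1 reflects non-collapsibility: the two models estimate different hazard ratios. All of this stands.

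A reader might infer that the omission makes the noninferiority test too easy, or hides harm. The documents do not support that. Section 11.9 does not define 1.38 as conditional on risk, and against its own ratio the planned model holds about its nominal level (step 4). At the planning ratio of 0.95 the shift works slightly against noninferiority, and at 1.00 there is none. The 6.9% figure needs a very strong assumed score. Equally, nothing in section 11.9 establishes that the margin is marginal, and the planned ratio is already conditional on dose adjustment.

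Other points stand in part. The documents support antiplatelet therapy as a predictor of bleeding but give no data that STS predicts NACE. Antiplatelet therapy may change after randomization (5.1.1), so the declaration describes later exposure only roughly; it remains a legitimate baseline covariate. Section 11.2 allows no imputation, so an incomplete score could drop a subject from the ITT model; a stated rule answers this. Sections 11.2 and 11.6 leave further analyses to the SAP, so an adjusted analysis may appear there, but it would not be the primary test.

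A region term might also seem natural because Japan has a different INR target. That target applies only to VKA subjects aged 70 or over. It could modify the treatment effect, and a main-effect covariate would not address that.

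**Conclusion.** The point holds as a modest improvement, not as a flaw in validity. The primary model uses one covariate although others are recorded at baseline. The cost is about 0.4 to 3.6 points of H3 power under an assumed hazard ratio of 0.65, about 130 to 143 bleeds and a score SD of 0.5 to 0.7. Real gains are probably at the low end, because the simulations adjust for the complete score. H4 would gain in the same direction; its gain was not quantified.

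For noninferiority, the consequence depends on how the margin is read. If 1.38 is conditional on baseline risk and true harm lies at that value, the error rate is about 3 to 4% instead of 2.5% at SD 0.5 to 0.7. If 1.38 refers to the ratio from the planned model, there is no material inflation. In the simulations adjustment cost nothing at 0.95. The plan should settle the reading of the margin either way.

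**What to change.** In sections 11.4 and 11.4.1, and in the matching synopsis text, add fixed baseline covariates next to dose adjustment for H1 to H4: pre-declared antiplatelet therapy from IXRS (none, single, dual), STS score and HAS-BLED score. Compute the scores from information that predates allocation, since the trial is open-label.

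State a simple rule for missing score elements, set without reference to arm or outcome, so that no ITT subject is dropped; a fixed fill-in value with a missing indicator would do. Write it as an explicit exception to the no-imputation statement in section 11.2. State that the 1.38 margin applies to the hazard ratio from this model. Report the current model as a sensitivity analysis.

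The cost is wording in the protocol and SAP, with no new data collection. Section 11.10 finalizes the SAP before database lock; the covariates should be fixed as early as possible, because choosing them late in an open-label trial would be less credible. The downside is that the reported hazard ratio becomes conditional on these covariates.

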MI	Myocardial infarction
mITT	Modified intention to treat
MLBCs	Major late bleeding complications
NACE	Net adverse clinical events
NSAID	Nonsteroidal anti-inflammatory drug
OAC	Oral anticoagulant(s)
OAP	Oral antiplatelet
PACT-Q	Perception of Anticoagulant Treatment Questionnaire
PCI	Percutaneous coronary intervention
P-gp	P-glycoprotein
PP	Per protocol
PT	Preferred Term
SAE	Serious Adverse Event
SAF	Safety analysis set
SAP	Statistical Analysis Plan
SAPT	Single antiplatelet therapy
SEE	Systemic embolic event
SmPC	Summary of product characteristics
SOP	Standard operating procedures
STS	Society of Thoracic Surgeons
SUSAR	Suspected Unexpected Serious Adverse Reaction
TAVI	Transcatheter aortic valve implantation
TEAE	Treatment-emergent adverse event
TEE	Transesophageal echocardiography or transesophageal echocardiogram
TEG	Thromboelastography
TIMI	Thrombolysis in Myocardial Infarction
TTE	Transthoracic echocardiography or transthoracic echocardiogram
ULN	Upper limit of normal
VKA	Vitamin K antagonist
WBCT	Whole blood clotting time
WHO	World Health Organization

DEFINITIONS SPECIFIC TO THIS PROTOCOL

Term	Definition for this protocol
Discontinuation	Permanent stoppage of study medication. The subject will not be allowed to restart study medication and should follow the transition procedures outlined in Section 5.2.1.1.2 or Section 5.2.1.2.2.
Interruption	A temporary stoppage of study medication. The subject is allowed to restart the study medication at the discretion of the Investigator.
End of TAVI	The clock for randomization starts with the removal of the sheath with hemostasis
End of Study	As an event driven study, enrollment will be stopped no later than at the attainment of a total of 320 subjects experiencing an adjudicated NACE across the combined treatment arms, and , the study will continue until the last subjects enrolled will have accomplished the minimum treatment duration of at least 6 months plus their Post-treatment Follow-up Visit. This Visit by the last subject enrolled will be defined as the end of the study (or common study end date [CSED]).
Major bleeding	Major bleeding is considered to include life-threatening and fatal bleeding.
Study drugs	Any study medication or prescribed oral antiplatelet (OAP) co-administered medication is defined within this protocol as a study drug.

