5.8. Subject Withdrawal/Discontinuation

The intended duration of the two treatment regimens is up to 36 months. Subjects must stay on the assigned OAC-based regimen as much as possible.

Discontinuation of the assigned regimen is mandatory if the CrCL falls below 15 mL/min on two consecutive occasions or if subject is placed on dialysis. If the Investigator doubts the accuracy of the CrCL value calculated with the Cockcroft-Gault formula (Section 17.7), he/she may consider calculating CrCL using a 24-hour urine collection, for confirmatory purposes. If a subject's CrCL, calculated with either the Cockcroft-Gault formula or 24-hour urine collection, recovers to > 15 mL/min, the subject should resume study regimen in line with the applicable labels.

For subjects with a suspected transient decrease in CrCL < 15 mL/min it is recommended that repeat testing of CrCL occur after corrective action is taken or when the medical condition that caused the worsening renal function resolves. The timing of the repeat testing is at the discretion of the Investigator and will vary depending on the nature of the medical condition (e.g., 1-2 weeks for urinary tract infection or over diuresis vs. several weeks to months for glomerulonephritis).

If other clinical contraindications for any study medication develop (according to the label of the respective drug), the study medication must be discontinued (or dose decreased if applicable). If the contraindication resolves, the respective study medication is restarted. During each interruption of anticoagulant or antiplatelet therapy, subjects are evaluated to determine whether the subject can safely resume the study drug. A post-randomization change in health status that results in the subject meeting one or more of the exclusion criteria should only lead to interruption or discontinuation of the assigned medications if the change in health status implies a contraindication according to the drug labels.

Study medications are permanently discontinued if the subject refuses continuation of any medication in the assigned study regimens.

All subjects are followed through to the termination of the study irrespective of changes in the antithrombotic regimen. Clinical follow-up before the end of the study is only terminated at the explicit documented request of the subject or his/her death.

All study drug start and stop dates are captured in eCRF together with the reason for interruption or discontinuation.

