'Initial dose to Final Dose + 30 days': This period is defined as the time-period between the date and time of initial dose of study Edoxaban or study VKA and the date and time of final dose of study Edoxaban or study VKA + 30 days, including study regimen interruptions.

Follow-up is censored at the last date of known follow-up status in subjects with incomplete follow-up. Investigators are instructed to complete follow-up as much as possible irrespective of changes or discontinuation of study medication.

When using the ITT analysis set, the reference date is the date and time of randomization, whereas in mITT and PP analyses, the reference date is the date and time of first intake of study Edoxaban or study VKA.

The main analyses of adjudicated primary and secondary exploratory endpoints (Section 7.2, Section 7.3, and Section 7.4, respectively) will be based on ITT analysis set and takes the first adjudicated event during the 'overall study period' into account.

However, in supplemental analyses, other combinations of analysis sets and analysis periods may be considered to evaluate the robustness of the main analyses on adjudicated safety or efficacy endpoints. Details on these analyses will be described in the SAP.

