11.10. Statistical Process

The statistical analysis will be performed by the assigned CRO under the guidance of the Daiichi Sankyo study biostatistician.

A Statistical Analysis Plan will be written providing all the details on the statistical methods and definitions for the analysis of the efficacy and safety data, as well as describing the approaches to be taken for summarizing other clinical study information such as, but not limited to, subject disposition, demographic and baseline characteristics, study drug exposure, and prior and concomitant medications.

To preserve the integrity of the statistical analysis and clinical study conclusions, the SAP will be finalized prior to database lock.

All statistical analyses will be performed using SAS[®] Version 9.3 or higher (SAS Institute, Cary, NC 27513).

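### If Kaplan-Meier is used with deaths censored, the descriptive cumulative rate of ISTH major bleeding will be modestly overstated; the protocol names no competing-risk estimator

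*Combined protocol and SAP*

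**What the plan says.** Section 11.4 gives one method for cumulative rates: "For time to first event analyses, cumulative event rates over time are summarized using the Kaplan-Meier method as appropriate". Section 11.4.1, which covers the two primary endpoints, repeats it: "For time to first event analyses based, cumulative event rates over time are summarized using the Kaplan-Meier method as appropriate". The synopsis carries the same sentence. Competing risks and cumulative incidence are not mentioned.

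On censoring, section 11.2 says in general terms that subjects who do not reach an endpoint are censored, and adds: "Follow-up is censored at the last date of known follow-up status in subjects with incomplete follow-up". Section 11.4 says that subjects without an event "will be censored at the last date of the analysis period or at the last date of known outcomes status", the second option being for those with incomplete follow-up. Death has no rule of its own. Section 5.8 says when observation stops: "Clinical follow-up before the end of the study is only terminated at the explicit documented request of the subject or his/her death".

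Two further passages set limits. The protocol-specific definitions state: "Major bleeding is considered to include life-threatening and fatal bleeding". Section 11.10 leaves the remaining detail to a later document: "A Statistical Analysis Plan will be written providing all the details on the statistical methods and definitions". That document is to be final before database lock. The text available for this review contains no separate SAP.

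**The concern.** One minus Kaplan-Meier equals the share of subjects who have had the event only if the censored subjects could still have it later. A subject who has died cannot have a major bleed. Treating that death as ordinary censoring estimates how many would bleed if nobody died of anything else, and this figure is never below the share who actually bleed.

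Major bleeding is the endpoint where this matters most, because its curve accompanies a confirmatory endpoint and readers will take it as the proportion of subjects who bled. Fatal bleeds count as events, so only deaths without a preceding or causal major bleed compete. The same applies to the exploratory endpoints that leave out some or all deaths (stroke, MI, SEE, valve thrombosis, cardiovascular mortality, MACE, MACCE), with a smaller absolute excess where events are rare. Every version of NACE includes all-cause death, so NACE and all-cause mortality have no competing death.

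**Working it through.** **Inputs from the protocol.** NACE rate of 14% per year on VKA and median follow-up of two years (section 11.9); about 1400 subjects randomized 1:1, so 700 per arm; minimum treatment of 6 months for the last subjects enrolled (synopsis). The protocol states no cumulative bleeding rate, so there is no planned figure to reproduce.

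**Assumptions.** Constant hazards per year: b for major bleeding (0.04-0.10) and d for death without a major bleed (0.02-0.10), with b + d no more than 0.14. The cap follows from the NACE definition. The first of major bleed or death is itself a NACE, so it cannot come before the first NACE. Under constant hazards, its hazard therefore cannot exceed that of NACE.

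**Formulas at time T.**
- One minus Kaplan-Meier, deaths censored: 1 - exp(-bT)
- Cumulative incidence: b/(b+d) x [1 - exp(-(b+d)T)]

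**Worked case, b = 0.06, d = 0.08, T = 2.** Kaplan-Meier: 1 - exp(-0.12) = 11.31%. Cumulative incidence: (0.06/0.14) x (1 - exp(-0.28)) = 0.4286 x 0.2442 = 10.47%. Excess: 0.84 points.

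| b, d (per 100 patient-years) | 2 years: KM vs cumulative incidence (excess) | 3 years: KM vs cumulative incidence (excess) |
|---|---|---|
| 4, 2 (smallest excess) | 7.69% vs 7.54% (0.15) | 11.31% vs 10.98% (0.33) |
| 8, 2 | 14.79% vs 14.50% (0.28) | 21.34% vs 20.73% (0.60) |
| 5, 5 | 9.52% vs 9.06% (0.45) | 13.93% vs 12.96% (0.97) |
| 6, 8 | 11.31% vs 10.47% (0.84) | 16.47% vs 14.70% (1.77) |
| 6.75, 7.25 (largest excess) | 12.63% vs 11.77% (0.85) | 18.33% vs 16.54% (1.80) |

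Over the whole range the relative excess is about 2-10% at 2 years and 3-15% at 3 years. A simulation with 2,000,000 subjects per case gave 0.45 for 5/5 and 0.84 for 6/8 at 2 years, matching the formulas.

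**If 14% is a one-year risk.** The hazard is then -ln(1 - 0.14) = 0.151. With b + d capped there, the largest excess is about 1.0 point at 2 years and 2.0 at 3 years.

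**Against sampling error.** Assume follow-up uniform over 0.5-3.5 years, which has a median of 2, and 700 per arm. The Greenwood standard error is exp(-bT) x sqrt{(1/700) x integral from 0 to T of b/[exp(-(b+d)t) G(t)] dt}, with G(t) = 1 before 0.5 years and (3.5 - t)/3 after. It comes to about 1.2-1.7 points per arm at 2 years and 1.7-2.5 at 3 years. The excess is 0.1-0.6 standard errors at 2 years and 0.2-0.8 at 3 years.

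**Between arms at 3 years, b = 0.06 in both.** The Kaplan-Meier difference is 0. With d = 0.07 vs 0.08 the true difference in cumulative incidence is 14.91% - 14.70% = 0.21 points; with d = 0.06 vs 0.08 it is 15.12% - 14.70% = 0.42 points.

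**The case against.** The strongest reply is that the protocol does not commit to the error. Kaplan-Meier is to be used only as appropriate, other summary statistics are promised as well, and an SAP is still to come. This stands, and it makes the point conditional. A reader might infer that the published bleeding rate is certain to be too high. The documents do not support that, because they leave room for another estimator even though they name none.

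Second, censoring at death is inferred. Section 5.8 governs observation, not analysis, and section 11.4 also allows censoring at the end of the analysis period. If subjects who died stayed in the risk set until then, one minus Kaplan-Meier would estimate cumulative incidence and the excess would vanish. The Cox model for major bleeding would then estimate a subdistribution hazard ratio. Censoring at death is the more natural reading, because a death leaves follow-up incomplete. The ambiguity is real, however, and is itself a reason to write the rule down.

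Third, the size rests on assumed rates. This stands. It can also be argued that the NACE rate sets no ceiling, because bleeds and deaths that follow a non-fatal MI or stroke are not first NACE. That part fails under constant hazards, for the ordering reason given with the assumptions.

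Finally, the excess is below one standard error and nothing confirmatory changes. Both are true. The excess is nevertheless systematic: it always goes upward, grows with follow-up and does not shrink with sample size.

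**Conclusion.** The point holds in conditional form. If Kaplan-Meier is applied to ISTH major bleeding with deaths censored at death, the descriptive cumulative rate is too high. Under the stated assumptions the excess is about 0.15-0.85 points at 2 years and 0.3-1.8 at 3 years, or up to about 1.0 and 2.0 if 14% is a one-year risk. The direction is certain given that reading. The size is illustrative, because the documents give neither a bleeding rate nor a death rate for the trial.

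A reader might go further and infer that the noninferiority or superiority conclusions on bleeding are biased. The documents do not support this. All four tests use the confidence interval of the Cox hazard ratio, and with deaths censored at death that is a valid cause-specific hazard ratio. Between-arm differences in the curves move little unless mortality differs materially by arm. This is a reporting improvement that is nearly free, and it does not threaten the trial's conclusions.

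**What to change.** In sections 11.4 and 11.4.1 (and the matching synopsis sentence), or in the SAP before database lock:

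- Estimate the cumulative incidence of ISTH major bleeding, and of the other endpoints that do not include all-cause death, by the Aalen-Johansen estimator, with deaths outside the endpoint as the competing event.
- Keep Kaplan-Meier for all versions of NACE and for all-cause mortality.
- State that deaths outside the endpoint are censored at the date of death in the Cox model, so that its hazard ratio is plainly cause-specific.

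The cost is a few lines of text and standard code. Reported cumulative rates for these endpoints become slightly lower. The hypothesis tests, sample size and data collection do not change.
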